17.1 Data management

Once consented into the study, participants will be given a unique ID number. Once the participant is randomised into the study, they will be assigned a unique randomisation ID number. Both ID's will be kept on a log.

All data will be entered onto the REDCap system. Paper CRFs will be available in cases where the online system is offline. Once online again, the data will be entered and the paper CRFs filed away.

Exported data will be pseudo anonymised and only contain a participant ID number. Data will be reported as per the analysis plan.

17.2 Source data

Data will be recorded directly to a database using online REDCap. We will develop a REDCap database that will provide a secure web application, accessible via HTTPS/SSL, which is fully NHS toolkit compliant. Users will be issued with a username and password and will be required to login for web application access; their activity will be tracked using unique user identities and their access to data controlled by defined access roles.

A paper backup system will be established in case of technical failure. Where paper CRFs are used, they will be entered onto the database as soon as it is available, and the paper copy will be filed away.

Elements of the REDCap database will include:

- Consent
- Registration
- Eligibility screening
- Dates
- Randomisation and arm allocation
- Baseline and weekly questionnaires
- Follow-up questionnaires
- AE and SAE forms
- Withdrawal from study
- Study product dispensing

Validation rules will be applied to ensure the validity and quality of the data. The database will have an audit trail. All study staff will be trained on how to use the database, and this will be logged on a training log. Personal identifiable data (PID) will be collected on an instance of REDCap which is fully NHS toolkit compliant, and also stored on a password protected, encrypted file with restricted access to authorised staff only. When the research database is exported for analysis this will be in de-identified form, with no PID included.

Surveys will either be completed directly by participants, or by suitably trained research staff, as designated in the site delegation log, as accurately and completely as possible throughout the study.

Direct access will be granted to authorised representatives from the Sponsor, host institution and the regulatory authorities to permit trial-related monitoring, audits and inspections.

17.3 Confidentiality

The Chief Investigator has a responsibility to ensure that participant anonymity is protected and maintained. They must also ensure that their identities are protected from any unauthorised parties. Information with regards to study participants will be kept confidential and managed in accordance with the General Data Protection Regulation (GDPR) 2018, NHS Caldicott Guardian, The Research Governance Framework for Health and Social Care and Research Ethics Committee Approval. All trial data will be stored in line with the Medicines for Human Use (Clinical Trials) Amended Regulations 2006 and the General Data Protection Regulation (GDPR) 2018 and archived in line with the Medicines for Human Use (Clinical Trials) and all subsequent amendments as defined in the JRMO SOP 20 Archiving.

The Chief Investigator and the study team will adhere to these parameters to ensure that the Participant's identity is protected at every stage of their participation within the study. At time of consent each participant will be allocated a unique participant number (by the online database system). When randomised into the study, each participant will have a unique randomisation number.

Identifiable data will also be collected on an instance of REDCap which is fully NHS toolkit compliant and also stored on a password protected, encrypted file with restricted access to authorised staff only. This is required to allow weekly phone calls and follow-up data collection. This will include name, address, email, telephone number, NHS number and date of birth. Only study personnel, the study sponsor and relevant regulatory authorities will have access to study data. When the research database is exported for analysis this will be in de-identified form, with no PID included.

All information will be kept confidential. Copies of all documents regarding the study will be kept in the trial master file (TMF) and/or relevant site file.

17.4 Record Retention and Archiving

During the course of research, all records are the responsibility of the Chief Investigator and must be kept in secure conditions. When the research trial is complete, it is a requirement of the Research Governance Framework and Sponsor Policy that the records are kept for a further 25 years.

All paper information relevant to the study will be archived and retained for 25 years at the Barts Health NHS Trust facility in [name]. Electronic CRF data (which will not include personal identifiable data) will be kept on a secure database for 25 years, following the sponsors SOP on electronic archiving.

Destruction of essential documents will require authorisation from the Sponsor.

18. Interventions and tools

18.1 Devices

N/A

18.2 Techniques and interventions

See section 10.1 for interventions.

18.3 Tools

We will be using the European Quality of Life-5 Dimensions (EQ5D) (20), Fagerstrom Test of Cigarette Dependence (FTCD) (18), items from the Mood and Physical Symptoms Scale (MPSS) (19) and the Smoking cessation services and health service use questionnaire. All are validated measure used frequently in this area of research. The respiratory questions used to gauge change during treatment have been developed by the research team and have been used to report changes in respiratory outcome in two RCTs.

See section 10.2 for study measures.

19. Safety reporting

19.1 Adverse Events (AEs) and Adverse Reactions (ARs)

An AE is any untoward medical occurrence in a participant to whom an intervention has been administered, including occurrences which are not necessarily caused by or related to that intervention. An AE can therefore be any unfavourable or unintended sign (including an abnormal laboratory finding), symptom or disease temporally associated with study activities.

An AR is any untoward and unintended response in a participant to an intervention. All AE judged by either the reporting investigator or the sponsor as having a reasonable causal relationship to the intervention qualify as AR. The expression 'reasonable causal relationship' means in general that there is evidence or an argument to suggest a causal relationship.

19.2 Notification and reporting of Adverse Events and Reactions

Data on AEs, ARs, SARs and SAEs will be collected. If the AE/AR is **not** defined as SERIOUS, it will be recorded in the CRF and the participant will be followed up by the research team if not resolved. All AEs, ARs and SAEs will be documented in the e-CRF.

19.3 Serious Adverse Events (SAEs) or reactions

A serious adverse event (SAE) is defined as an untoward occurrence that:

- Results in death,
- Is life-threatening,
- Requires hospitalisation or prolongation of existing hospitalisation,
- Results in persistent or significant disability or incapacity,
- Consists of a congenital anomaly or birth defect, or
- Is otherwise considered medically significant by the investigator.

SARs will be reported to the REC where in the opinion of the Chief Investigator the event was serious and:

- Related (it may have resulted from administration of any of the research interventions), and
- Unexpected (the type of event is not listed in the protocol or other Reference Safety Information as an expected occurrence).

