19.5 Recording of Adverse events or Reactions

The following are considered expected AEs/ARs:

Symptoms which are potentially caused by EC which include; dislike of taste, cough and mouth/throat irritation.

All AEs and ARs will be recorded in e-CRF and the participant followed up by the research team to resolution or end of trial. AE's will begin to be recorded from receipt of the study product by the participant until the end of the follow-up period.

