19.6 Notification and reporting of Serious Adverse Events

Serious Adverse Events (SAEs) that are considered to be ‘related’ and ‘unexpected’ will be reported to the sponsor within 24 hours of learning of the event, and to the REC within 15 days in line with the required timeframe.

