19.8 Notification and Reporting of Serious Adverse Events/Reactions

All SAEs including SARs will be recorded in the subjects’ notes, the CRF, the sponsor SAE form and reported to the co-ordinating site. **Related and unexpected SAE's should be reported to the sponsor** at [contact]

within 24 hours of PI or co-investigators becoming aware of the event. Nominated co-investigators can be authorised to sign the SAE forms in the absence of the CI at the co-ordinating site or the PI at the participating sites. The original and any subsequent follow-up of SAE Forms must be kept with the investigator site file at the study site.

Additionally related and unexpected SAE's will be reported to the Ethics committee within 15 days.

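### Expectedness is judged by event type alone, so as written a serious e-cigarette-related event of a listed type is exempt from the 24-hour sponsor report and the 15-day REC report

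*Protocol*

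**What the plan says.** Four parts of Protocol section 19 bear on this.

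- **Section 19.3** sets the REC trigger: "SARs will be reported to the REC where in the opinion of the Chief Investigator the event was serious and" meets two further conditions, being related and being unexpected. The second is defined as "Unexpected (the type of event is not listed in the protocol or other Reference Safety Information as an expected occurrence".
- **Section 19.5** supplies the list. Under the lead-in "The following are considered expected AEs/ARs" it gives "Symptoms which are potentially caused by EC which include; dislike of taste, cough and mouth/throat irritation". It sets no grade, outcome or seriousness limit.
- **Section 19.6** gives the time limits. SAEs that are both related and unexpected "will be reported to the sponsor within 24 hours of learning of the event, and to the REC within 15 days".
- **Section 19.8** repeats both limits, the second as "Additionally related and unexpected SAE's will be reported to the Ethics committee within 15 days". It also has a wider rule for every SAE, whether expected or not: the event is entered in the notes, "the CRF, the sponsor SAE form and reported to the co-ordinating site".

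**The concern.** An expected list normally spares the sponsor and the ethics committee urgent reports of familiar, minor reactions. Here the list is joined to a definition that looks only at the kind of event. Nothing in that definition asks whether the event was worse than the reaction the authors had in mind when they listed it. Section 19.4.3 grades severity as mild, moderate or severe, but the expectedness test does not use the grade.

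At stake is the speed with which people outside the co-ordinating team hear of a serious reaction. Cough and mouth/throat irritation are two of the three reactions the protocol itself anticipates from e-cigarettes. Respiratory symptoms are a secondary endpoint at all three follow-ups (section 6.5), and section 9.1 has smokers identified in inpatient and outpatient settings. A listed symptom that becomes serious is an event on which prompt outside review would be useful, and the rule as written does not ask for it.

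**Working it through.** No sample size, power or error rate bears on this point, so the check is to trace one case through the rules and then test whether the text allows another reading.

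**Trace.** Take a participant in an e-cigarette arm who is admitted to hospital with cough judged to be caused by the device.

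| Question | Rule | Answer |
|---|---|---|
| Serious? | 19.3: hospitalisation qualifies | Yes |
| Related? | 19.3: may have resulted from a research intervention | Yes, by assumption |
| Type listed in the protocol? | 19.5: cough is listed | Yes |
| Unexpected? | 19.3: only if the type is not listed | No |
| Sponsor report within 24 hours? | 19.6, 19.8: needs related and unexpected | Not due |
| REC report within 15 days? | 19.3, 19.6, 19.8: needs related and unexpected | Not due |
| Sponsor SAE form, CRF, co-ordinating site? | 19.8: all SAEs | Yes |
| e-CRF? | 19.2: all SAEs | Yes |

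Mouth/throat irritation gives the same answers. Dislike of taste would too, though it is hard to see it meeting a seriousness criterion.

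**Does the label AEs/ARs confine the list to non-serious events?** Three places in the same section point the other way.

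1. Section 19.1 defines AE and AR with no ceiling on seriousness.
2. Section 19.2 gives a handling rule for an AE/AR that is not serious, and section 19.4.1 has adverse events and reactions assessed for seriousness. Both presuppose that an AE/AR can be serious.
3. Expectedness has a stated consequence only in sections 19.3, 19.6 and 19.8, all of which concern serious events. If the list in 19.5 did not reach serious events, it would have no effect anywhere in the protocol.

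**Could other Reference Safety Information close the gap?** No. Under the definition in 19.3, a further document can only add listed types. It cannot remove one that the protocol already lists.

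**Size.** Two of the three arms are sent an e-cigarette: 390 + 390 = 780 of the 1,170 participants planned in section 12.1. The documents give no rate for serious cough or serious mouth/throat irritation, so the expected number of affected events cannot be calculated. It may well be small.

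**The case against.** The strongest reply is that the list was never meant for serious events. It is headed AEs/ARs, its items are called symptoms, and it sits in a section on recording AEs and ARs, while serious events have sections of their own. Section 19.2 also names SAEs and SARs separately from AEs and ARs when it wants to cover all of them. This is a fair account of what the authors may have intended. But the text does not state the limit, and the usage set out above is against it. What stands is that the defect may be one of drafting and not of intent.

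The second reply is that other safeguards remain, and this stands in full. A reader might infer that such an event never reaches the sponsor or the REC. The documents do not support that:

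- Every SAE goes on the sponsor SAE form and to the co-ordinating site (19.8) and into the e-CRF (19.2).
- The sponsor has direct access to the data (17.2) and agrees a monitoring plan with on-site monitoring at least yearly (section 20).
- A DMEC meets every 6 to 12 months (section 21).
- The Chief Investigator must tell the sponsor and the REC at once if urgent safety measures are taken (19.7).
- An annual progress report goes to both (19.9). Its SAE content is not described, so by that route REC notification is neither assured nor excluded.

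Apart from the urgent-measures rule, which is triggered by the measures and not by the event, none of these routes carries the expedited time limits.

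Two other inferences go too far. One is that serious respiratory events as a class are exempt. The test concerns the type of event, so a serious respiratory event recorded as some other type is not among the three named symptoms and, on that list, remains unexpected. The other starts from section 19.1, where "All AE judged by either the reporting investigator or the sponsor as having a reasonable causal relationship to the intervention qualify as AR", and concludes that every SAE form must be forwarded to the sponsor. That sentence defines an adverse reaction and promises no routine forwarding. Sending all forms would be a different reporting policy and would not correct a contradiction.

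**Conclusion.** The point holds in a limited form. Taken together, sections 19.3 and 19.5 make a serious, e-cigarette-related event of a listed type expected by definition, and sections 19.6 and 19.8 then require no expedited report of it. What is lost is the 24-hour report to the sponsor and the 15-day report to the REC. Recording, reporting to the co-ordinating site, sponsor access and DMEC oversight are not lost.

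The conclusion rests on applying the definition literally and on reading AE/AR in section 19.5 as it is used elsewhere in section 19. If the authors intended the list for non-serious events only, the remedy is the same, because the protocol needs to say so. The exemption covers a narrow set of event types and its frequency cannot be estimated from the documents. It is nevertheless created by rule in the trial's safety reporting, and it is cheap to remove, so it should be corrected.

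**What to change.** Reconcile sections 19.3, 19.5, 19.6 and 19.8. The simplest way is one sentence in section 19.5 stating that the listed symptoms count as expected only when they are non-serious, so that a serious related event of a listed type is handled as unexpected for the reports in sections 19.6 and 19.8. A matching cross-reference in the definition in section 19.3 would remove any doubt about which text governs.

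The cost is a short protocol amendment and possibly a few more expedited reports. No new data collection is needed, because the SAE form is already completed for every SAE under section 19.8. Treatment, endpoints and analysis are unaffected.

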19.4 Investigators Assessment

19.4.1 Seriousness

Adverse event/reactions will be assessed for seriousness according to the definitions given in section 19.3.

19.4.2 Causality

The causality of all serious adverse events/reactions will be assessed in relation to the trial treatment by the CI and study team.

19.4.3 Severity

The severity of the event/reaction will be assessed according to the following terms and assessments. The intensity of an event should not be confused with the term “serious” which is a regulatory definition based on patient/event outcome criteria.

Mild: Some discomfort noted but without disruption of daily life

Moderate: Discomfort enough to affect/reduce normal activity

Severe: Complete inability to perform daily activities and lead a normal life

19.5 Recording of Adverse events or Reactions

The following are considered expected AEs/ARs:

Symptoms which are potentially caused by EC which include; dislike of taste, cough and mouth/throat irritation.

All AEs and ARs will be recorded in e-CRF and the participant followed up by the research team to resolution or end of trial. AE's will begin to be recorded from receipt of the study product by the participant until the end of the follow-up period.

19.6 Notification and reporting of Serious Adverse Events

Serious Adverse Events (SAEs) that are considered to be ‘related’ and ‘unexpected’ will be reported to the sponsor within 24 hours of learning of the event, and to the REC within 15 days in line with the required timeframe.

19.7 Urgent Safety Measures

The CI will take urgent safety measures if necessary to ensure the safety and protection of the clinical study participant from immediate hazards to their health and safety. The measures will be taken immediately. The approval of the REC prior to implementing urgent safety measures is not required. However, the CI will inform the sponsor and Research Ethics Committee (via telephone) of this event immediately.

The CI will inform the REC in writing within 3 days, in the form of a substantial amendment. The sponsor (Joint Research Management Office (JRMO)) will be sent a copy of the correspondence with regards to this matter.

19.8 Notification and Reporting of Serious Adverse Events/Reactions

All SAEs including SARs will be recorded in the subjects’ notes, the CRF, the sponsor SAE form and reported to the co-ordinating site. **Related and unexpected SAE's should be reported to the sponsor** at [contact]

within 24 hours of PI or co-investigators becoming aware of the event. Nominated co-investigators can be authorised to sign the SAE forms in the absence of the CI at the co-ordinating site or the PI at the participating sites. The original and any subsequent follow-up of SAE Forms must be kept with the investigator site file at the study site.

Additionally related and unexpected SAE's will be reported to the Ethics committee within 15 days.

19.9 Annual Safety Reporting

The CI will send the Annual Progress Report to the REC using the HRA template (the anniversary date is the date on the REC “favourable opinion” letter) and to the sponsor.

19.10 Overview of the Safety Reporting responsibilities

The CI will ensure that safety monitoring and reporting is conducted in accordance with the sponsor's requirements.

20. Monitoring and auditing

The sponsor or delegate retains the right to audit any study, study site, or central facility. Any part of the study may be audited by the funders, where applicable.

A Trial Monitoring Plan will be developed and agreed by the Sponsor and Chief investigator based on the sponsor's trial risk assessment; this will include on site monitoring by the co-ordinating site (QMUL) at least once a year.

21. Trial committees

A **Trial Management Group** (TMG) comprising selected co-investigators, and key employed staff will meet as required to check on the practical details of the trial and progress. The mix of co-investigators who attend will vary between meetings, depending on the stage of the trial and the priorities at different stages of the project. The CI will attend all meetings.

External oversight will be provided by a **Trial Steering Committee** (TSC), who will convene during the pilot recruitment phase and every 12 months thereafter. The TSC would be formed of a Chair (Independent), Chief Investigator, study manager, 2 service users (independent), as SSS specialist and an independent statistician.

A Data Monitoring and Ethics Committee (DMEC) will also be convened every 6-12 months, formed of a Chair (independent), independent statistician and independent expert.

22. Finance and funding

The study is funded by the National Institute for Health Research (NIHR).

23. Indemnity

The insurance that Queen Mary University of London has in place provides cover for the design and management of the study as well as "No Fault Compensation" for participants, which provides an indemnity to participants for negligent and non-negligent harm.

24. Dissemination of research findings

